9.4 Analysis of Vital Signs

Vital sign measurements of systolic and diastolic blood pressure, pulse rate, body temperature, and weight will be summarized.

Each vital sign variable will be summarized for all time points with the number of non-missing observations, mean and standard deviation, median, minimum and maximum. Mean change from Baseline to each applicable post-Baseline visit will be summarized for each vital sign variable, with the number of observations, Baseline mean, and visit mean. The change from Baseline mean, standard error, and 95% confidence interval will be presented for the mean change from Baseline within each treatment group.

Vital sign variables will be evaluated based on potentially clinically important (PCI) criteria ([Appendix C](#)). For each vital sign PCI criterion, the number and percentage of subjects who have a vital sign value meeting the criteria will be summarized. Listings will be provided to summarize subject-level vital sign data for subjects meeting PCI criteria.

9.5 Safety Subgroup Analyses

No planned safety subgroup analyses.

9.6 Other Safety Analyses

ECG is collected at Screening and Weeks 64, 80, and 96. The number and percentage of subjects with QTcF prolongation (QTcF > 500 msec) will be summarized by treatment groups using Safety Analysis Set population.

10.0 Other Analyses

No other analyses are planned.

11.0 Interim Analysis

11.1 Interim Analysis

No interim analysis is planned.

11.2 Data Monitoring Committee

An internal safety DMC composed of persons independent of the Study M19-130 and Study M20-186 protocols and with relevant expertise in their field will review unblinded safety data from the ongoing studies. The primary responsibility of the DMC will be to protect the safety of the subjects participating in Study M19-130 and in this study. When needed, high-level unblinded efficacy data may also be requested by the DMC and reviewed so that the DMC can assess benefit:risk of any emerging safety differences.

A separate DMC charter for Studies M19-130 and M20-186 was prepared outside of the protocols and described the roles and responsibilities of the DMC members, frequency of data reviews, planned interim analyses, relevant safety data to be assessed, and expectations for blinded communications for Studies M19-130 and M20-186.

12.0 Overall Type-I Error Control

No hypothesis tests will be conducted for the efficacy analysis.

13.0 Version History

Table 1. SAP Version History Summary

Version	Date	Summary
1.0	12 August 2020	Original version
2.0	02 January 2024	
1. Updated to align with the updates in the protocol after M19-130 interim analysis.2. Update analysis of study drug duration and analysis of safety to use M20-186 data only. Integrated data will be summarized later in the submission of SLE Phase 3 program.

Appendix A. Protocol Deviations

The number and percentage of subjects who reported at least one of the following protocol deviation categories will be provided.

- Subject entered into the study even though s/he did not satisfy entry criteria.
- Subject developed withdrawal criteria during the study and was not withdrawn.
- Subject received wrong treatment or incorrect dose of study.
- Subject took prohibited concomitant medication.

Appendix B. Definition of Adverse Events of Special Interest

Adverse Events of Special Interest (AESI) will be identified using the following search criteria:

AESI	Type of MedDRA Query	Broad or Narrow Search	SMQ/CMQ Search Criteria
Serious Infections	CMQ		"Infections" – Subset for SAEs
Opportunistic Infection excluding Tuberculosis and Herpes Zoster	CMQ		"Opportunistic Infection" excluding Tuberculosis and Herpes Zoster CMQ
Herpes Zoster	CMQ		"Herpes Zoster"
Active Tuberculosis	CMQ		"Active Tuberculosis"
Possible Malignancy	SMQ	Narrow	"Malignancies"
Malignancy	SMQ	Narrow	"Malignant Tumours"
Malignancies excluding NMSC	SMQ	Narrow	"Malignant Tumours" removing NMSC output
Non-Melanoma Skin Cancer (NMSC)	SMQ	Narrow	"Skin Malignant Tumours" removing Melanoma CMQ
Adjudicated GI perforations			Based on adjudicated results (the identification of events to be adjudicated are described in the GI Perforation charter)
Adjudicated cardiovascular events: MACE*		Output from CAC	
Cardiovascular Death			
Non-fatal Myocardial Infarction			
Non-fatal Stroke			
Undetermined/Unknown Cause of Deaths			
Other Cardiovascular events			
Anemia	CMQ		"Non-Hemolytic and Non-Aplastic Anemias"
Neutropenia	CMQ		"Hematological Toxicity – Neutropenia"
Lymphopenia	CMQ		"Hematological Toxicity - Lymphopenia"

AESI	Type of MedDRA Query	Broad or Narrow Search	SMQ/CMQ Search Criteria
Renal dysfunction	SMQ	Narrow	"Acute Renal Failure"
Hepatic disorders	SMQ	Narrow	"Drug Related Hepatic Disorders"
Adjudicated Thrombotic Events: VTE**	Output from CAC		
Deep Vein Thrombosis			
Pulmonary Embolism			
Other Venous Thrombosis			

* MACE: Major Adverse Cardiovascular Events, defined as cardiovascular death, non-fatal myocardial infarction and non-fatal stroke.

** VTE: Venous thromboembolic events, defined as deep vein thrombosis (DVT) and pulmonary embolism (PE) (fatal and non-fatal).

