Identified risks for upadacitinib are summarized in the upadacitinib Investigator's Brochure⁸ and include: serious infections, opportunistic infections and tuberculosis (TB), and herpes zoster. Potential risks for upadacitinib include: malignancies, including lymphoma and non-melanoma skin cancer (NMSC), gastrointestinal (GI) perforations, major adverse cardiovascular events (MACE), hematologic changes (anemia, neutropenia, and lymphopenia), increased serum creatinine and renal dysfunction, hepatic events and increased hepatic transaminases, elevated creatine phosphokinase (CPK), embolic and thrombotic events (non-cardiac, non-central nervous system [CNS]), and fetal risks.

As of 15 December 2019, 171 healthy volunteers have received at least 1 dose of elsubrutinib; the most common side effect reported was headache, mild in severity.

As of 06 May 2020, from the Phase 2 RA and SLE studies, there are no identified safety risks for elsubrutinib or for ABBV-599 (elsubrutinib/upadacitinib) combination.

A detailed description of the preclinical pharmacology, metabolism, and toxicology datasets can be found in the elsubrutinib⁹ and upadacitinib⁸ Investigator's Brochures. The results of genetic toxicology testing indicate that elsubrutinib and upadacitinib are not genotoxic. Preclinical embryofetal development studies indicate that elsubrutinib and/or upadacitinib are embryotoxic, fetotoxic, and/or teratogenic.

Systemic lupus erythematosus patients are known to have an increased risk of thrombosis. Based on this and the potential risk of thrombosis with the use of JAK inhibitors, the use of estrogen-containing

contraceptives may further increase the risk of thrombotic events; therefore, the choice of contraceptive should be carefully considered.

In LTE Study M20-186, benefit/risk assessment of treatment groups for rollover may require subjects to be reassigned or discontinued based on the outcome of the unblinded interim analysis from the feeder Study M19-130 (See Section 4 Investigational Plan). Routine safety evaluations of all treatment groups will be performed. These include assessments of deaths, serious adverse events (SAEs), non-serious adverse events (AEs), withdrawals, and pregnancies, as well as routine monitoring by physical examinations, vital sign measurements, electrocardiograms, (ECGs), and clinical laboratory testing (hematology, chemistry, and urinalysis).

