3.4 Safety Endpoints

The following safety evaluations will be performed for the entire study duration as measures of safety and tolerability:

- AE monitoring
- Physical examinations
- Vital sign measurements
- ECGs
- Clinical laboratory testing (hematology, chemistry, and urinalysis)

Serious adverse events will be assessed at any dose that results in a death, inpatient hospitalization or prolongation of existing hospitalization, persistent or significant disability/incapacity, or a congenital anomaly (see Section 6.1 for more details).

The following areas of safety interest will be routinely assessed to identify any major safety findings related to immunosuppression or potential risks associated with the individual classes of therapy: serious and/or opportunistic infections, herpes zoster, active TB, malignancies (all types), adjudicated GI perforations, adjudicated cardiovascular events (e.g., MACE), anemia, neutropenia, lymphopenia, renal dysfunction, hepatic disorders, and adjudicated embolic and thrombotic events (non-cardiac, non-CNS) including venous thromboembolic events defined as pulmonary embolism and deep vein thrombosis (see Section 6.1 for more details).

Specific toxicity management measures will be utilized, as described in Section 6.2, for serious infections, serious GI events, cardiovascular events (MACE), malignancy, ECG abnormalities, and select laboratory abnormalities. In addition, a 30-day follow-up phone call from the last dose of study drug should occur to determine the status of any ongoing AEs/SAEs, or the occurrence of any new AEs/SAEs.

Additional safety monitoring measures include an independent Cardiovascular Adjudication Committee (CAC) (see Section 6.1) and an internal DMC (see Section 6.3).

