The following adverse events of special interest (AESI) will be routinely monitored during the study:

- Serious infections
- Opportunistic infections
- Herpes zoster
- Active TB
- Malignancy (all types)
- Adjudicated GI perforations
- Adjudicated cardiovascular events (e.g., MACE)
- Anemia
- Neutropenia
- Lymphopenia
- Renal dysfunction
- Hepatic disorders
- Adjudicated embolic and thrombotic events (non-cardiac, non-CNS) including venous thromboembolic events defined as pulmonary embolism and deep vein thrombosis.

Adverse Event Severity and Relationship to Study Drug

Investigators will rate the severity of each AE according to the National Cancer Institute (NCI) Common Terminology Criteria for Adverse Events (CTCAE) version 5, which can be accessed at: https://ctep.cancer.gov/protocoldevelopment/electronic_applications/docs/ctcae_v5_quick_reference_8.5x11.pdf.

If no specific grading criteria are provided for the reported event, then the event should be as follows:

- Mild (Grade 1): asymptomatic or mild symptoms; clinical or diagnostic observations only; intervention not indicated;
- Moderate (Grade 2): minimal, local or noninvasive intervention indicated; limiting
 age-appropriate instrumental activities of daily living (ADL) (instrumental ADL refer to preparing
 meals, shopping for groceries or clothes, using the telephone, managing money, etc.);
- Severe (Grade 3 5):
 - Grade 3: severe or medically significant but not immediately life-threatening; hospitalization or prolongation of hospitalization indicated; disabling; limiting self-care ADL (self-care ADL refers to bathing, dressing and undressing, feeding self, using the toilet, taking medications, and not bedridden);

- Grade 4: Life-threatening consequences; urgent intervention indicated;
- Grade 5: Death related to AE.

The investigator will use the following definitions to assess the relationship of the AE to the use of study drug:

| Reasonable Possibility | After consideration of factors including timing of the event, biologic plausibility, clinical judgment, and potential alternative causes, there is sufficient evidence (information) to suggest a causal relationship. |
|------------------------------|--|
| No Reasonable Possibility | After consideration of factors including timing of the event, biologic plausibility, clinical judgment, and potential alternative causes, there is insufficient evidence (information) to suggest a causal relationship. |

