Subjects must be discontinued from study drug for an ECG change considered clinically significant and with reasonable possibility of relationship to study drug OR a confirmed absolute QTcF value > 500 msec or confirmed increase of ≥ 60 msec from Baseline.

Management of Muscle-Related Symptoms

If a subject experiences symptoms suggestive of myositis or rhabdomyolysis, CPK and aldolase measurements should be requested and will be provided after review by the AbbVie TA MD with clinical management and/or study drug interruption as deemed appropriate by the treating physician. Please refer to Table 4 below for further instructions.

Management of Thrombosis Events

Subjects who develop symptoms of thrombosis should be promptly evaluated and treated appropriately. If the diagnosis of deep vein thrombosis, pulmonary embolus, or non-cardiac, non-neurologic arterial thrombosis is confirmed, the subject must be discontinued from study drug.

Management of Select Laboratory Abnormalities

For any given laboratory abnormality, the investigator should assess the subject and apply the standard of care for medical evaluation and treatment following any local guidelines. Specific toxicity management guidelines for abnormal laboratory values are described in Table 4 and may require a supplemental eCRF to be completed (see Section 6.1). All abnormal laboratory tests that are considered clinically significant by the investigator will be followed to a satisfactory resolution. If a repeat test is required per Table 4, the repeat testing must occur as soon as possible.

Table 4. Specific Toxicity Management Guidelines for Abnormal Laboratory Values

| Laboratory Parameters | Toxicity Management Guidelines | |
|---------------------------------|--|--|
| Hemoglobin | If hemoglobin < 8 g/dL, interrupt study drug dosing and confirm by repeat testing with a new sample. | |
| | If hemoglobin decreases ≥ 3.0 g/dL from Baseline without an alternative etiology, interrupt study drug dosing and confirm by repeat testing with new sample. | |
| | • If hemoglobin decreases ≥ 3.0 g/dL from Baseline and an alternative etiology is known, the subject may remain on study drug at the investigator's discretion. | |
| | If confirmed, continue to withhold study drug until hemoglobin value returns to normal reference range or its baseline value. | |

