9.2.6 Adverse Events of Special Interest

Adverse events of special interest (AESI) will be summarized by SOC and PT and will be based on standardized or company MedDRA queries (SMQs or CMQs). AESI are categorized in [Appendix B](#). Tabular listings of AESIs will be provided.

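### The protocol's anemia AESI has no qualifier, but the SAP identifies it with a query that by its title leaves out hemolytic and aplastic anemias, and no other AESI row covers them

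*SAP*

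**What the plan says.** Protocol Section 3.4 names the areas of safety interest, among them "anemia, neutropenia, lymphopenia, renal dysfunction, hepatic disorders". The AESI list in Protocol Section 6.1 also has anemia as a bare entry. Protocol Section 2.2 counts anemia among the potential hematologic risks of upadacitinib. Protocol Section 7.4 commits to summarizing AESIs as percentages and as events per 100 patient-years.

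SAP Appendix B then sets the operational definitions: "Adverse Events of Special Interest (AESI) will be identified using the following search criteria". The row labelled Anemia has a single entry, the company query "Non-Hemolytic and Non-Aplastic Anemias". The terms in that query are not listed in either document, and the SAP does not explain its scope. SAP Section 9.2.6 builds the AESI tables and listings from these queries.

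**The concern.** The label in the SAP table is broader than the search behind it. A reader of the study report who sees a row headed Anemia will take it to be the protocol's AESI, when two classes of anemia were not searched for. Long-term safety is the primary objective of this study, and anemia is one of the drug risks that the protocol names.

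The protocol's hemoglobin rule in Table 4 (Section 6.2) shows how the two can diverge. It says "If hemoglobin < 8 g/dL, interrupt study drug dosing and confirm by repeat testing with a new sample", whatever the cause. An event could therefore interrupt dosing because of low hemoglobin, be coded to an excluded term, and not be counted in the anemia AESI.

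**Working it through.** **1. How Appendix B treats exclusions elsewhere.** Two other AESIs are narrowed by a named exclusion.

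| SAP row | Part left out of the search | Exclusion in the row label? | Own row for the excluded part? |
|---|---|---|---|
| Opportunistic infection | Tuberculosis, herpes zoster | Yes | Yes, one each |
| Malignancies excluding NMSC | Non-melanoma skin cancer (NMSC) | Yes | Yes |
| Anemia | Hemolytic, aplastic (from the query title) | No | No |

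Malignancy also has an overall row beside its two parts. The anemia row follows neither practice.

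**2. Where an event coded to an excluded term would and would not appear.**

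Missing from:
- the anemia AESI tables and listings (SAP 9.2.6) and the listing of subjects with treatment-emergent AESIs (SAP 9.2.9), as an anemia entry;
- the AESI row of the overview (SAP 9.2.2), unless the subject has another AESI. The matching rate counts events, so another AESI would contribute that other event and not the anemia.

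Still present in:
- the tables by System Organ Class and Preferred Term (SOC/PT), including those by relationship and by toxicity grade (SAP 9.2.1, 9.2.3);
- the serious event and discontinuation tables and listings, if the event qualifies (SAP 9.2.5, 9.2.9);
- the hemoglobin summaries, changes and shifts (SAP 9.3). Hemoglobin is also in the counts of potentially clinically important values, but the criterion there is worded as greater than Grade 3 or greater than Grade 4, which read literally leaves out Grade 3.

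**3. Sensitivity to one case.** Inputs: 65 projected subjects in each of 5 arms (Protocol 4.1); 60-80% rollover (Protocol 7.7); a 1:1 split of former placebo subjects between Groups 5a and 5b (Protocol 4.1, SAP 2.3).

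The plan's own total is reproduced: 5 × 65 = 325, 0.60 × 325 = 195 and 0.80 × 325 = 260, which is the stated 195 to 260.

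Assuming the same rollover in every arm and no arm dropped:
- Groups 1-4: n = 65 × 0.60 = 39 to 65 × 0.80 = 52. One case is 1/39 = 2.6% to 1/52 = 1.9%.
- Groups 5a and 5b: n = 39/2 = 19.5 to 52/2 = 26. One case is 1/19.5 = 5.1% to 1/26 = 3.8%.

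This shows how far one case moves a percentage. It is not an expected loss, because neither document gives an incidence for any form of anemia.

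**The case against.** The strongest reply is that this is operationalization, not contradiction. Protocol Section 7.1 leaves the details of analysis to the SAP, so choosing a query for an unqualified label is the SAP's job. The mechanism discussed in Protocol Section 2.2 is inhibition of erythropoiesis, which does not describe hemolysis, and hemolytic anemia can be lupus activity. This supports a deliberate choice of scope, but the SAP states neither the scope in its label nor a reason for it.

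A second reply is that the events remain visible. This is correct and limits the consequence. A serious case would reach the serious event tables. SAP Section 9.2.7 also tabulates events in more than 2% of any group. On the sizes above, one case passes that mark in Groups 5a and 5b, and in Groups 1-4 whenever the group has fewer than 50 subjects (1/50 = 2.0%). What these outputs do not do is add such events to an anemia total.

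A third reply is that Protocol Section 6.1 keeps worsening lupus out of adverse event collection unless the outcome is serious. A non-serious hemolytic anemia judged to be lupus would not be an adverse event, and a wider query would not recover it. That stands. It also means that the hemolytic anemias that are recorded are those not attributed to worsening lupus or those with serious outcomes, so the exclusion cannot be defended as removing only lupus activity.

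**Conclusion.** The mismatch is real and worth correcting. Its consequence is moderate: it affects the AESI outputs of a descriptive study with no hypothesis test, and the events can be found elsewhere in the report. The number of cases affected cannot be estimated. The per-case figures rest on equal rollover and on all arms continuing, and SAP Sections 5.0 and 8.1 say the groups may change.

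Four stronger readings are tempting and are not supported:
- A reader might infer that the protocol defines the AESI as anemia of any type. It says only anemia, and adds a note that all types count only to malignancy.
- A reader might infer that every hemolytic or aplastic case is lost. The exclusion is read from a query title, and a case coded to an unspecified anemia term could still be counted.
- A reader might infer that a missed case would show only as one Preferred Term line. The outputs listed above say otherwise.
- A reader might infer that such a case always ends treatment under Table 4. The rule quoted is an interruption with repeat testing, and applies only if hemoglobin meets the trigger. The companion rule for a fall of at least 3.0 g/dL does depend on cause.

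**What to change.** In SAP Appendix B:
- keep the present query, with the row label changed to *Anemia, non-hemolytic and non-aplastic*;
- add a separate row for hemolytic and aplastic anemias;
- report an *Anemia (any)* total as the protocol's AESI.

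This is the arrangement Appendix B already uses for malignancy, with an overall row and its parts. A lesser alternative is to relabel the present row and state why its scope is limited. That would remove the mislabelling but leave the protocol's AESI without a matching count.

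The cost is one or two extra rows, with no new data collection. Some hemolytic cases will reflect lupus rather than drug. The separate row keeps these visible, so the total can be read with that in mind.

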- Subject with latent TB who is non-compliant with or refuses to initiate TB prophylaxis.
- The subject becomes pregnant while on study drug.
- Malignancy, except for localized NMSC or CIS of the cervix.
- Subject is significantly non-compliant with study procedures, including inconsistent study drug
 dosing, which would put the subject at risk for continued participation in the trial as determined
 by the investigator or the AbbVie TA MD.
- Subject develops a GI perforation.
- If a diagnosis of deep vein thrombosis, pulmonary embolus, or non-cardiac, non-neurologic arterial thrombosis is confirmed.
- Subject develops active neuropsychiatric SLE (excluding lupus headache) as defined by the CNS portion of SLEDAI-2K or BILAG.
- Subject develops Class IV lupus nephritis (confirmed by biopsy).

In order to minimize missing data for efficacy and safety assessments, subjects who prematurely discontinue study drug treatment should, if possible:

- Continue in the study without receiving study drug
- Have all procedures performed outlined in the PD visit, preferably within 2 weeks of study drug discontinuation
- Continue with their regular study visit schedule

All attempts must be made to determine the date of the last study drug dose and the primary reason for discontinuation of study drug or study participation. The information will be recorded on the appropriate electronic case report form (eCRF) page. However, these procedures should not interfere with the initiation of any new treatments or therapeutic modalities that the investigator feels are necessary to treat the subject's condition. Following discontinuation of study drug, the subject should be treated in accordance with the investigator's best clinical judgment.

For subjects to be considered lost to follow-up, reasonable attempts must be made to obtain information on the subject's final status. At a minimum, 2 telephone calls must be made and 1 certified letter must be sent and documented in the subject's source documentation.

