For causality assessments, events assessed as having a reasonable possibility of being related to the study drug will be considered "associated." Events assessed as having no reasonable possibility of being related to the study drug will be considered "not associated." In addition, when the investigator has not reported a causality or deemed it not assessable, AbbVie will consider the event associated.

If an investigator's opinion of no reasonable possibility of being related to study drug is given, an "Other" cause of event must be provided by the investigator for the SAE.

In Japan, the Principal Investigator will provide documentation of all SAEs to the Director of the investigative site and to the Sponsor.

Cardiovascular Adjudication Committee

An independent CAC will adjudicate all blinded cardiovascular and cerebrovascular events, embolic/thrombotic events, and deaths, as defined in the CAC charter.

Pregnancy

While not an AE, pregnancy in a study subject must be reported to AbbVie within 24 hours after the site becomes aware of the pregnancy. Subjects who become pregnant during the study must be discontinued from the study drug (Section 5.5). If a pregnancy occurs in a study subject or in the partner of a study subject, information regarding the pregnancy and the outcome will be collected.

In the event of pregnancy occurring in a subject's partner during the study, written informed consent from the partner must be obtained prior to collection of any such information. AbbVie will provide a separate consent form for this purpose. Pregnancy in a subject's partner will be collected from the date of the first dose in LTE Study M20-186 through 30 days following the last dose of study drug.

The pregnancy outcome of an elective or spontaneous abortion, stillbirth, or congenital anomaly is considered an SAE and must be reported to AbbVie within 24 hours after the site becomes aware of the event.

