7.4 Statistical Analyses for Safety

All safety analyses will be performed on the Safety Analysis Set.

All treatment-emergent adverse events (TEAEs), SAEs, AEs leading to discontinuation, and AESI will be collected during the study. A TEAE is defined as an event with onset or worsening after the first study dose of study drug and within 30 days after the last dose of study drug administration. The number and percentages of subjects experiencing TEAEs will be tabulated using the Medical Dictionary for Drug Regulatory Activities (MedDRA®) System Organ Class (SOC) and preferred term (PT). Summaries (including percentages and events per 100 patient-years) of SAEs, deaths, AEs leading to discontinuation, and AESI will be provided as well. For selected laboratory and vital sign parameters, mean change from Baseline and the percentage of subjects with evaluations meeting pre-defined criteria for Potentially Clinically Important values will be summarized.

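### SAP Appendix B names only venous components under adjudicated thrombotic events, so no stated row gives the protocol's wider embolic and thrombotic AESI or its non-venous part

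*SAP*

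**What the plan says.** **Protocol.** Section 6.1 lists among the AESIs "Adjudicated embolic and thrombotic events (non-cardiac, non-CNS) including venous thromboembolic events defined as pulmonary embolism and deep vein thrombosis". Section 3.4 names the same category for routine assessment. Section 5.5 names part of what lies outside VTE, in a stopping rule that begins "If a diagnosis of deep vein thrombosis, pulmonary embolus, or non-cardiac, non-neurologic arterial thrombosis is confirmed". Section 2.2 lists the whole category as a potential upadacitinib risk. The Cardiovascular Adjudication Committee (CAC) adjudicates, among other things, "embolic/thrombotic events, and deaths, as defined in the CAC charter". Section 7.4 states the output: "Summaries (including percentages and events per 100 patient-years) of SAEs, deaths, AEs leading to discontinuation, and AESI will be provided as well".

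**SAP.** Appendix B gives the criteria by which AESIs are identified. Its thrombotic block is headed "Adjudicated Thrombotic Events: VTE", takes its source from CAC output, and lists deep vein thrombosis (DVT), pulmonary embolism (PE) and other venous thrombosis. A footnote limits VTE to DVT and PE. The cardiovascular block, also from CAC output, includes a row "Other Cardiovascular events" with no definition. Section 9.2.2 ties the AESI overview count and rate to Appendix B, and Section 9.2.6 refers to it for the AESI categories.

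**QTcF.** SAP 9.6 counts subjects with QTcF above 500 msec and nothing else. Protocol 5.5 and 6.2 use that limit or a confirmed increase of at least 60 msec.

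**The concern.** Longer-term safety is the primary objective, and the protocol cites thrombosis as a risk both of lupus and of JAK inhibition. An AESI summary on this topic should match the category that the protocol defines. A programmer who follows Appendix B has rows for venous events only. The protocol's combined count and rate would have to be assembled by someone who noticed the difference, and an adjudicated peripheral arterial event has no named place in the thrombotic block. Readers of the study report could then take a VTE figure for the full embolic and thrombotic figure.

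**Working it through.** **1. Side by side.**

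| Element | Protocol | SAP |
|---|---|---|
| Category | All adjudicated non-cardiac, non-CNS embolic and thrombotic events (3.4, 6.1) | No row with this content (Appendix B) |
| VTE | A subset, defined as PE and DVT | Named in the block heading; footnote says DVT and PE |
| Other venous thrombosis | Inside the category, not in VTE as defined | Listed in the VTE block, outside the footnote's definition |
| Non-venous events | Inside the category; arterial thrombosis named in 5.5 and 6.2 | No row |
| Output | Percentages and rates per 100 patient-years (7.4) | Overview count and rate tied to Appendix B (9.2.2) |

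The word that decides the protocol's meaning is the one introducing VTE in "adjudicated embolic and thrombotic events (non-cardiac, non-CNS) including venous thromboembolic events": VTE is included in the category and does not exhaust it.

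**2. Was the narrowing deliberate?** The SAP version history records two changes for version 2.0: alignment with the protocol after the feeder study's interim analysis, and restriction of the drug-duration and safety analyses to M20-186 data. It records no change to this AESI.

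**3. Are the data there?** Protocol Table 3 lists a dedicated supplemental form for non-cardiac, non-CNS embolic and thrombotic events, and Section 6.1 sends such events to the CAC with no stated venous limit.

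**4. Scale of one event.** No incidence is given, so only the weight of a single event can be shown.

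- Plan's figure: 5 groups × 65 = 325 subjects; 0.60 × 325 = 195 and 0.80 × 325 = 260, as stated in Protocol 7.7 and SAP 2.4.
- Exposure by the SAP 9.2.4 formula, if everyone completes 56 weeks (392 days): 195 × 392 / 365.25 = 209.3 and 260 × 392 / 365.25 = 279.0 patient-years.
- One event overall: 100 / 209.3 = 0.48 and 100 / 279.0 = 0.36 per 100 patient-years.
- One continuing group, assuming the same 60% to 80% rollover of 65: 39 to 52 subjects, 41.9 to 55.8 patient-years, so one event is 2.39 to 1.79 per 100 patient-years.

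Full exposure is an upper case. With less exposure, each event weighs more.

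**5. QTcF.** A rise r from baseline b meets the 60 msec criterion without exceeding 500 msec when 60 ≤ r ≤ 500 − b. With an illustrative b of 400, that is 60 to 100 msec. Such a subject is not in the SAP 9.6 count.

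**The case against.** A reader might infer that non-venous events would go unreported, or that the SAP rules them out as AESIs. The documents support neither.

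- **Events appear elsewhere.** They enter the tables by system organ class and preferred term, and the serious adverse event tables if serious. Because Protocol 5.5 makes confirmed non-cardiac, non-neurologic arterial thrombosis a reason to stop study drug, on-drug cases should also reach the discontinuation table and listing. This stands. These outputs do not give the adjudicated combined count or rate.
- **They may already be AESIs.** Protocol Table 3 files the embolic and thrombotic form under cardiovascular events, so the row "Other Cardiovascular events" could hold arterial cases and bring them into the overall AESI count and listing. This stands as a possibility. The row is undefined, and Protocol 6.1 lists cardiovascular and non-cardiac thrombotic events as separate AESIs, so it would still not return the protocol's category.
- **The heading can be read more widely.** In the cardiovascular block, the text before the colon is the category and MACE only a component, since other rows fall outside the MACE footnote. Read alike, the thrombotic heading could be the wide category with VTE as a component. That is a fair reading, but the rows actually listed are still all venous.
- **The CAC charter is not among the documents.** It may settle the categories. That limits the claim to what Appendix B states.
- **SAP 9.2.2 allows further tabulations.** They are discretionary and do not meet the commitment in Protocol 7.4.

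It is also tempting to treat the QTcF omission as a contradiction. It is not: Protocol 7.4 promises criteria-based summaries for laboratory and vital sign parameters, not for ECGs.

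**Conclusion.** The mismatch is real and minor. Protocol 3.4, 6.1 and 7.4 define and promise a summary of all adjudicated non-cardiac, non-CNS embolic and thrombotic events. Appendix B names venous components only, so no stated row gives that count and rate or the non-venous part. The conclusion rests on the text of Appendix B as extracted, with the charter unseen.

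No size of undercount follows from the documents. Any probability that a non-venous event occurs would rest on a rate that they do not give. The figures above show only what one event would weigh. The study tests no hypothesis, so no formal decision depends on the row. What is at stake is whether the primary safety summary matches its own definition.

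The QTcF count is a separate, optional improvement.

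**What to change.** In SAP Appendix B:

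1. Add, from the CAC output, a row for all adjudicated non-cardiac, non-CNS embolic and thrombotic events and a row for the non-venous ones, and keep VTE as a sub-row. Report counts, percentages and events per 100 patient-years.
2. Define "Other Cardiovascular events" so that no event is missed or counted twice.
3. State whether other venous thrombosis counts in the VTE total, given the footnote.
4. Check these categories against the CAC charter before finalising.

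Optionally, in SAP 9.6, add the number and percentage of subjects with a QTcF increase of at least 60 msec. State whether confirmation is required and which Baseline applies. For former placebo subjects, SAP 9.1 uses the last value before M20-186 dosing, Protocol 5.5 refers to the M19-130 Baseline, and Protocol 6.2 says only Baseline. These passages must be reconciled for that row.

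The cost is a few table rows and lines of definition. The events already have a collection form and go to adjudication, and the ECGs are already scheduled. Whether the CAC output carries a separate non-venous category is the one thing to verify.
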